1. BACKGROUND

Myelofibrosis (MF) (including primary MF, post-polycythemia vera [PV] MF and post-essential thrombocythemia [ET] MF) is a clonal myeloproliferative neoplasm, characterized by progressive bone marrow fibrosis and subsequent ineffective erythropoiesis, dysplastic megakaryocyte hyperplasia, and extramedullary hematopoiesis. The typical clinical presentation includes marked splenomegaly, progressive anemia, and constitutional symptoms. Bone marrow transplant is the only curative treatment for MF, but the procedure is associated with high morbidity and mortality (Stewart et al. 2010; Ballen 2012). Bone marrow fibrosis resolves in subjects after successful transplant as early as one month (Przepiorka et al. 1998).

Before 2011, there was no approved medical therapy for MF and most symptomatic subjects were managed with various combinations of growth factors, immunomodulatory agents, cytotoxic chemotherapy, and steroids. For many subjects, these therapies were not effective at all or were associated with transient alleviation of certain symptoms of the disease. Ruxolitinib is a Janus kinase inhibitor, approved in the United States (US) and European Union (EU) for the treatment of subjects with intermediate or high-risk myelofibrosis, including primary myelofibrosis (PMF), post-polycythemia vera myelofibrosis (post-PV MF) and post-essential thrombocythemia (post-ET MF) (JAKAFI® Full Prescribing Information 2011). Treatment with ruxolitinib results in reduction in spleen volume and improvement in constitutional symptoms. However, ruxolitinib is not believed to be disease modifying and does not have convincing effects on bone marrow fibrosis (Verstovsek et al. 2012). Futhermore, >20% of subjects discontinue ruxolitinib due to intolerance or lack of efficacy within the first year of therapy (Palandri et al. 2020). Other Janus kinase inhibitors are in clinical development and fedratinib was approved by US Food and Drug Administration (USFDA) in 2019 (Blair 2019). There is a clear unmet medical need for new therapies for MF, in particular therapies that are potentially disease modifying and improve bone marrow function.

Pentraxin-2 (PTX-2), also known as serum amyloid protein is an endogenous protein that circulates in the bloodstream. Recent discoveries about the biology of tissue repair and fibrosis have elucidated the important role that PTX-2 plays biologically in regulating processes that relate to scar prevention and healing. PTX-2 is an agonist that binds to Fc gamma receptors on monocytes and promotes their differentiation into regulatory macrophages (Mreg), which function to promote epithelial healing and resolution of inflammation and scarring. PTX-2 also prevents the differentiation of monocytes into M2 pro-fibrotic macrophages and fibrocytes, preventing the formation of fibrosis. rhPTX-2 (recombinant human pentraxin-2, RO7490677) is a recombinant version of human pentraxin-2 (rhPTX-2). Similar to endogenous PTX-2, rhPTX-2 circulates as a non-covalent, homo-pentameric glycoprotein. Pre-clinical and clinical data support the investigation of rhPTX-2 in the treatment of fibrotic diseases (Murray et al. 2010; Pilling et al. 2007; Raghu et al. 2018; Verstovsek et al. 2016; Duffield et al. 2010).

Study BO42355 was developed to examine the efficacy and safety of rhPTX-2 in intermediate-1, intermediate-2, and high risk subjects with PMF, post-PV MF, or post-ET MF subjects. More details regarding the study are provided in the Appendix 1, Appendix 2, Appendix 3, and Appendix 4 (Protocol Synopses for the various study stages).

Of note, rhPTX-2 was developed by Promedior and acquired by Roche in 2020. Detailed Statistical Analysis Plans (SAPs) (Stage 1 Version 2.0: 11 April 2019; Stage 2 Version 2.0: 5 March 2018) were prepared by Promedior and signed prior to the respective Stage 1 and Stage 2 primary database lock (DBL) and analyses. This present SAP was prepared by Roche and signed before the final DBL of the Stage 1 and Stage 2 open label extensions (OLEs) of the study. The aim of this SAP is to highlight the analyses that will be performed for the final analysis and reported in a Clinical Study Report (CSR) for both main Stage 1 and Stage 2, and inclusive of their respective OLEs.

2. STUDY DESIGN

Study BO42355 is a Phase II study, divided into 2 stages: Stage 1 and Stage 2, each with a respective OLE.

[figure not shown]
The objective of Stage 1 was to evaluate the efficacy of two different dose schedules of rhPTX-2 in subjects with DIPSS defined intermediate-1, intermediate-2, or high risk PMF, post-PV MF, or post ET-MF. The two dosing schedules were tested as monotherapy and as an add-on therapy to subjects on a stable dose of ruxolitinib for at least three months.

The objective of the Stage 2 was to determine the effect size of three different doses of monotherapy of rhPTX-2 on reduction in bone marrow fibrosis by > 1 grade at any time during the study in DIPSS intermediate-1, intermediate-2, and high risk subjects with PMF, post-PV MF, or post ET-MF who are anemic and/or thrombocytopenic and who are ineligible for, intolerant of, or have had an inadequate response to ruxolitinib.

Please see study design in

Figure 1 and more details in Appendix 1, Appendix 2, Appendix 3 and Appendix 4 (protocol synopses for the various study stages).

Figure 1 Study Design

PMF=Primary myelofibrosis; Post-ET=Post-Essential Thrombocythemia; PV MF=Polycythemia vera Myelofibrosis; RUX= Ruxolitinib.

Note: For Stage 1 and Stage 2 Open-Label Extension, subjects received rhPTX-2 10mg/kg.

In this document, reference to Stage 1 and Stage 2 will correspond to the main stage; otherwise, it will specify (i.e. OLE).

2.1 PROTOCOL SYNOPSIS

The Protocol Synopsis for each stage and OLE are in Appendix 1, Appendix 2, Appendix 3 and Appendix 4. For the Schedule of Assessments see Appendix 5 and Appendix 6.

2.2 EFFICACY ENDPOINTS

2.2.1 Primary Efficacy Endpoint

Stage 1:

The primary endpoint for Stage 1 is the Overall Response Rate (ORR). Response rate is defined as the percent of subjects with a response as per International Working Group-Myeloproliferative Neoplasms Research and Treatment (IWG-MRT) criteria (assessed by the investigator), is defined as either:

• achieving clinical improvement (CI), partial remission (PR), or complete remission (CR) at a post-baseline assessment of treatment response

OR

 having at least stable disease (SD) for three consecutive end-of-cycle response assessments (e.g. Day 1 of the subsequent cycle) in conjunction with improvement in the bone marrow fibrosis score (as determined by adjudicated review) relative to baseline by at least one grade at any time point during the period of stable disease.

Stage 2:

The primary endpoint for Stage 2 is the bone marrow response rate (BMRR). Response rate is defined as the percent of subjects with a reduction in bone marrow fibrosis by at least one grade according to World Health Organization (WHO) criteria (see Appendix D of the protocol) from baseline to any time during the study as determined by a central adjudication panel of expert hematopathologists, blinded to subject, treatment, and time of biopsy.

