##### **7.11.6. Response Assessments**

Subjects will be assessed for response at Cycle 2 through Cycle 9. Response Assessments are based on International Working Group-Myeloproliferative Neoplasms Research and Treatment (IWG-MRT) criteria, to measure the overall response rate (ORR), defined as a clinical improvement (CI), partial remission (PR), and complete remission (CR) according to the International Working Group (IWG) Criteria ([APPENDIX B](#)).

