## APPENDIX B: International Working Group (IWG) consensus criteria for treatment response in myelofibrosis with myeloid metaplasia\*

Response categories	Required criteria (for all response categories, benefit must last for ≥12 wk to qualify as a response)
CR	Bone marrow: * Age-adjusted normocellularity; <5% blasts; ≤grade 1 MF† and Peripheral blood: Hemoglobin ≥100 g/L and <UNL; neutrophil count ≥ 1 × 10  /L and <UNL; Platelet count ≥ 100 × 10  /L and <UNL; <2% immature myeloid cells‡ and Clinical: Resolution of disease symptoms; spleen and liver not palpable; no evidence of EMH
PR	Peripheral blood: Hemoglobin ≥100 g/L and <UNL; neutrophil count ≥1 × 10  /L and <UNL; platelet count ≥100 × 10  /L and <UNL; <2% immature myeloid cells‡ and Clinical: Resolution of disease symptoms; spleen and liver not palpable; no evidence of EMH or Bone marrow: * Age-adjusted normocellularity; <5% blasts; ≤grade 1 MF†, and peripheral blood: Hemoglobin ≥85 but <100 g/L and <UNL; neutrophil count ≥1 × 10  /L and <UNL; platelet count ≥50, but <100 × 10  /L and <UNL; <2% immature myeloid cells‡ and Clinical: Resolution of disease symptoms; spleen and liver not palpable; no evidence of EMH
Clinical improvement (CI)	The achievement of anemia, spleen or symptoms response without progressive disease or increase in severity of anemia, thrombocytopenia, or neutropenia§
Anemia response	Transfusion-independent patients: a ≥20 g/L increase in hemoglobin level   Transfusion-dependent patients: becoming transfusion-independent¶
Spleen response#	A baseline splenomegaly that is palpable at 5-10 cm, below the LCM, becomes not palpable** or A baseline splenomegaly that is palpable at >10 cm, below the LCM, decreases by ≥50%** A baseline splenomegaly that is palpable at <5 cm, below the LCM, is not eligible for spleen response A spleen response requires confirmation by MRI or computed tomography showing ≥35% spleen volume reduction
Symptoms response	A ≥50% reduction in the MPN-SAF TSS††

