**Study Endpoints:****Primary:**

- The overall response rate (ORR), defined as a clinical improvement (CI), partial remission (PR), and complete remission (CR) according to the International Working Group (IWG) Criteria ([Appendix B](#))
- Stable disease with improvement in bone marrow fibrosis score by at least one grade according to the European Consensus on Grading of Bone Marrow Fibrosis ([Appendix D](#)) will also be considered a response (bone marrow response).

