- Myeloblasts and cellularity will be presented at baseline, Weeks 12 and 24 as well as change from baseline
- Collagen grade shifts relative to baseline at Weeks 12 and 24.

The modified MPN-SAF TSS will be presented descriptively at baseline and at the beginning of each cycle (Cycle 2 onward). In addition, the number of subjects with \geq 25% and \geq 50% reduction relative to baseline at the beginning of each cycle (Cycle 2 onward) will be presented.

Stage 2:

Duration of effect of the three doses on reduction in bone marrow fibrosis:

- To assess the duration of effect of the three doses on bone marrow improvement a
 Kaplan-Meier plot will be provided. Duration of BM improvement will be defined for
 responding subjects as time from first decrease from baseline of one grade to time of
 return to baseline levels. If no return to baseline levels then duration will be
 censored at the last BM assessment
- Effect and duration of effect of the three doses on disease related anemia, thrombocytopenia, and constitutional symptoms: For patients with improvement, the duration of improvement is defined as the number of weeks of improvement from the first12 weeks of improvement period.

IWG-MRT response will be summarized by treatment group at each visit by percent of subjects with complete response, partial response, clinical improvement, stable disease and progressive disease according to IWG-MRT criteria.

4.4.3 Exploratory Efficacy Endpoints

The exploratory endpoints will be summarized using tables, listings and graphs as appropriate.

4.4.4 Sensitivity Analyses

For Stage 2, a non-stratified analysis of BMRR will be computing as a sensitivity analysis.

4.4.5 **Subgroup Analyses**

Stage 1:

• Primary endpoint results will be presented by risks groups (intermediate-1, intermediate-2, or high risk subjects).

Stage 2:

- Primary endpoint results will be presented:
 - by risks groups (intermediate-1, intermediate-2, or high risk subjects)
 - for each strata separately (baseline anemia alone, baseline thrombocytopenia alone, baseline anemia and thrombocytopenia)
 - by transfusion status at baseline with transfusion dependency defined as: ≥ 2
 units PRBC every 4 weeks for 12 weeks prior to or after C1D1
 - by PTX-2 level at baseline classify by High/Low category (median as the cutoff)

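### SAP 2.2.1 does not carry Appendix B's 12-week duration rule into the Stage 1 CI/PR/CR definition, and SAP 4.4.2 does not say how unconfirmed IWG responses are classified by visit in Stage 2

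*SAP*

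**What the plan says.** Protocol Appendix B heads its response table with a condition on every category: "for all response categories, benefit must last for ≥12 wk to qualify as a response". The Stage 1 primary endpoint in Protocol Appendix K refers to that appendix, listing clinical improvement, partial remission and "complete remission (CR) according to the International Working Group (IWG) Criteria".

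SAP 2.2.1 opens the Stage 1 definition with a "response as per International Working Group-Myeloproliferative Neoplasms Research and Treatment (IWG-MRT) criteria (assessed by the investigator") and then gives two limbs. The first is "achieving clinical improvement (CI), partial remission (PR), or complete remission (CR) at a post-baseline assessment of treatment response", with no duration or confirmation. The second combines marrow improvement with "having at least stable disease (SD) for three consecutive end-of-cycle response assessments (e.g. Day 1 of the subsequent cycle"). SAP 4.4.1 tests the resulting rate against 10% in each of the four groups and overall, each at one-sided 5%.

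For Stage 2, SAP 2.2.2 keeps the protocol's secondary endpoint, the percentage of subjects in each IWG category. SAP 4.4.2 specifies its presentation: "IWG-MRT response will be summarized by treatment group at each visit by percent of subjects" in each category. Protocol 7.11.6 sets the timing: "Subjects will be assessed for response at Cycle 2 through Cycle 9". Protocol 8.5 adds an assessment at Cycle 9 Day 29.

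**The concern.** The SAP writes a persistence requirement into the study-specific limb (stable disease plus marrow improvement) and none into the CI/PR/CR limb. Elsewhere it states 12 consecutive weeks when it wants them, as in the Stage 2 hemoglobin criteria of SAP 2.2.2. A programmer working from the two limbs would flag a subject at the first visit recorded as CI, PR or CR. A programmer working from Appendix B would wait for 12 weeks of benefit. The two could obtain different response rates from the same data.

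This is the Stage 1 primary endpoint. Stage 1 is open-label, the investigator assigns the category, and a fall of at least 50% in a patient-reported symptom score is one route to CI. That route was used: Protocol 1.5 reports four IWG symptom responses at 36 weeks. The groups are small. With 27 subjects in four groups (27/4 = 6.75 on average), reclassifying one subject moves a group's rate by about 1/6.75 = 15 percentage points.

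In Stage 2 the first assessment falls at week 4, when 12 weeks of benefit is impossible. The SAP gives neither a rule for such a visit nor a per-subject sustained-response table.

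**Working it through.** **1. The design's own figures.** Protocol Appendix K states, per arm, type I error 3.4%, power at least 94% at a response rate of 0.4, 53% probability of stopping under the null, expected N 15 and maximum N 26. The second-stage increment is 20, so n1 = 26 − 20 = 6, continuing on at least one response. The final cut-off is in a figure not shown. At least 6 responses of 26 is the only cut-off among those tried (4 to 8) that matches both 3.4% and 94%.

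- Stop under the null: 0.9^6 = 0.531
- Expected N: 6 + (1 − 0.531) × 20 = 15.4
- Type I error at 0.10: 0.0339
- Power at 0.40: 0.938

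All reproduce. None depends on how long a response must last; they are tied to whatever event the 10% reference describes.

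**2. Timing.** SAP Appendix 5 places Stage 1 response assessments on Day 1 of Cycles 2 to 6: weeks 4, 8, 12, 16 and 20. A 12-week span needs four consecutive four-weekly assessments. Benefit first seen at week 4 can be followed to week 16, and at week 8 to week 20. Onset at week 12 needs week 24 (Cycle 6 Day 29), when blood counts, physical examination and the symptom form are collected although no response assessment is marked. Onset at week 16 or 20 needs extension data. In Stage 2, assessments run from week 4 to week 36, so onset up to week 24 can be confirmed in the main stage.

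**3. Direction.** Every sustained response is also an any-visit response, so the any-visit rate can only equal or exceed the sustained rate. The documents give no rate of transient responses, so the difference cannot be computed.

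**4. Illustration: transient events.** Assume a transient qualifying change with probability q at each of five independent visits. The chance of at least one is 1 − (1 − q)^5:

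| q | at least one |
|---|---|
| 1% | 4.9% |
| 2% | 9.6% |
| 3% | 14.1% |
| 5% | 22.6% |
| 10% | 41.0% |

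Positive correlation between visits lowers these figures.

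**5. Illustration: false success.** Assume 10% is the null rate for sustained response and any-visit counting raises it to p. The pooled test uses n = 27 (Protocol 5.1.1). With the standard error under the null it needs 6 responses: z = (6/27 − 0.1)/√(0.09/27) = 2.12. With a Wald 90% interval it needs 7: the lower bound is 9.1% at 6/27 and 12.1% at 7/27.

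| p | two-stage, ≥6 of 26 | pooled, ≥6 of 27 | pooled, ≥7 of 27 |
|---|---|---|---|
| 10% | 3.4% | 4.7% | 1.5% |
| 12% | 7.1% | 9.7% | 3.6% |
| 15% | 16.0% | 21.0% | 9.9% |
| 20% | 37.1% | 46.1% | 28.7% |

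**6. Rough bound from reported results.** Protocol 1.5 lists 10 marrow and 4 symptom responses at 36 weeks. Assuming a denominator of 27, no overlap and all four symptom responses transient, the overall rate would fall by at most 4/27 = 15 points. The remaining 10/27 = 37% has a 90% Wald lower bound of 0.370 − 1.645 × √(0.370 × 0.630/27) = 22%, above 10%. These are pooled 36-week counts; per-group and 24-week counts are not given.

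**The case against.** The strongest reply is that the rule is already there. SAP 2.2.1 defines a responder by the IWG-MRT criteria, and Appendix B makes 12 weeks a condition of qualifying. The stable-disease limb needed its own persistence rule because it is a study-specific addition with no IWG duration to inherit. An investigator applying Appendix B at week 4 could simply record stable disease. CI also requires more than a symptom change: no progression, no worsening of cytopenias, and minimum platelet and neutrophil counts. The anemia response in transfusion-dependent patients has a 12-week interval built in.

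Much of this stands. A reader might infer that the SAP abandons the 12-week rule. The documents do not support that: the rule is cited by reference and nowhere waived. A reader might also infer that the Stage 1 rate is in fact inflated. That is not shown, because the documents contain no transient-response data and investigators may already have applied the rule. Nor does Stage 2 replace the protocol endpoint with visit snapshots: SAP 2.2.2 retains it, and only the presentation is unresolved.

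What the reply does not settle is which rule is programmed. The limbs are the operational definition, and the first, read as written, is met at one visit. The pooled bound above suggests that the overall comparison with 10% may be robust, but it says nothing about the four group-level tests.

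There is also a fair point on timing. This SAP follows the Stage 1 primary analysis, for which an earlier Stage 1 SAP existed; whether that document fixed the derivation cannot be seen here.

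**Conclusion.** The point holds as an unresolved responder rule in a primary endpoint. For Stage 1, the CI/PR/CR limb omits the 12-week duration that its cited criteria require; read literally, one visit suffices and the response rate can be inflated. The amount is not computable and may be zero. The tabulated rates rest on assumed per-visit or null rates and show sensitivity only. For Stage 2, the gap is how an unconfirmed response is classified in a by-visit descriptive table; BMRR is unaffected. Because the SAP governs the final report of an investigator-assessed open-label endpoint, the rule should be written down.

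**What to change.** In SAP 2.2.1 (Stage 1) and 4.4.2 (Stage 2), count CI, PR or CR as an IWG response only when the criteria hold at consecutive assessments spanning at least 12 weeks. Use Cycle 6 Day 29 and open-label extension data, where available, to confirm late Stage 1 onsets. Flag any confirmation obtained after a schedule change or after stopping ruxolitinib, both of which Protocol Appendix L permits. State how a response too late to confirm is counted and how a visit with unconfirmed response is labelled. Tabulate best sustained IWG response per subject and arm. Report the any-visit rate beside it as a labelled sensitivity analysis, and state whether each comparison with 10% depends on the rule.

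The cost is SAP text and derivation programming; the main-stage assessments are already four-weekly. The downsides are real: the response rate may fall, some late-onset responses will stay unconfirmed (Stage 1 extension response assessments are only every third cycle from Cycle 10), and the change must be documented as made after the Stage 1 primary analysis. Reporting both rates lets the reader see the effect of that choice.

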2.2.2 Secondary Efficacy Endpoints

The secondary efficacy endpoints are as follows for:

Stage 1:

- Bone Marrow MF grade shifts relative to baseline over time
- Modified Myeloproliferative Neoplasm-Symptom Assessment Form Total Symptom Score (MPN-SAF TSS) changes from baseline over time

Stage 2:

- Bone Marrow improvement:
 - Bone marrow (BM) response rate (MF Grade) at each visit (reduction of 1 grade versus baseline)
 - Duration of BM response defined for responding subjects as time from first decrease from baseline of one grade to time of return to baseline levels. If no return to baseline levels or worse than baseline then duration will be censored at the last BM assessment.
- Hemoglobin improvement (number and percentage of subjects):
 - For red blood cell transfusion dependent subjects at baseline (at least 2 units every 4 weeks for 12 weeks prior to Cycle [C]1Day [D]1), improvement is defined as either:
 - 1) absence of any packed red blood cells (PRBC) transfusion during any consecutive 12 weeks interval with hemoglobin level of ≥80g/L

OR

- 2) at least a 50% reduction in PRBC transfusions for 12 consecutive weeks with hemoglobin level of ≥80g/L
- For red blood cell transfusion independent subjects improvement is defined as:
 - ≥10 g/L increase in hemoglobin level for 12 consecutive weeks without transfusions
- Platelet improvement (number and percentage of subjects)

- For transfusion dependent subjects at baseline, improvement is defined as either:
- 1) becoming transfusion independent for 12 consecutive weeks

OR

- 2) reduction in transfusions need ≥50% from baseline for 12 consecutive weeks
- For transfusion independent subjects with baseline platelet count below 100^9/L, improvement is defined as:
 - ≥50% increase in the number of platelet for 12 consecutive weeks or normalization of platelet count (above lower limit normal)
- Symptom improvement:

Percent of subjects with 50% reduction in MPN-SAF TSS from baseline over time(Tefferi 2013)

• Percent of subjects with complete response, partial response, clinical improvement, stable disease and progressive disease according to IWG-MRT criteria.

2.2.3 Exploratory Efficacy Endpoints

The exploratory efficacy endpoints are as follows for:

Stage 1:

- Bone marrow biopsy results for:
 - Myeloblasts (%), at each time point and change from baseline
 - Cellularity (%), at each time point and change from baseline
 - Collagen and reticulin grade shifts relative to baseline over time
- Modified MPN-SAF TSS
- Spleen size over time

Stage 2:

- Proportion of subjects with bone-marrow MF Grade 0 or 1 at 12, 24, and 36 weeks
- Proportion of subjects with 30% decrease, 30% increase, and stable (< 30% change) cellularity at 12, 24, and 36 weeks compared to baseline
- Change from baseline to Week 36 in hemoglobin for subjects with baseline < 100 g/L
- Number of units transfused in prior 12 weeks at baseline and Week 36 for transfusion dependent subjects
- Change from baseline to Week 36 in number of units transfused in prior 12 weeks for transfusion dependent subjects
- Proportion of subjects with increase from baseline to week 36 in hemoglobin (Hgb) from < 100 g/L to ≥ 100 g/L without transfusions
- Proportion of subjects with increase in Hgb from < 100 g/L at baseline to ≥ 100 g/L without transfusions for ≥ 12 consecutive weeks

- Number of units transfused in prior 12 weeks at baseline and Week 36 for platelet transfusion dependent subjects
- Proportion of subjects with increase from baseline to Week 36 in platelet from < 50 to
 ≥ 100 without transfusions
- Proportion of subjects with decrease from baseline to Week 36 in peripheral blood blasts from ≥ 1% to < 1%
- Percent of subjects with 10% reduction in spleen volume from baseline by computed tomography (CT) or magnetic resonance imaging (MRI) at each visit
- Percent of subjects with 35% reduction in spleen size volume from baseline by CT or MRI at each visit
- Change from baseline in spleen size volume by CT or MRI at each visit
- Percent of subjects with 10% reduction in liver volume from baseline by CT or MRI at each visit
- Percent of subjects with 35% reduction in liver size volume from baseline by CT or MRI at each visit
- Change from baseline in liver size volume by CT or MRI at each visit
- MPN-SAF total symptom score and change from baseline over time
- Mean change from baseline in European Organization for Research and Treatment of Cancer Quality of Life-Core 30 questionnaire (EORTC QLQ-C30) at 36 weeks
- Time to treatment failure (TTF) defined as either:
 - Any discontinuation from the study
 - Progressive disease
 - Study drug permanently stopped
 - Death

